### 17.2 Days 1-7 (Randomized, Double-Blind, Placebo-Controlled Treatment)

It is hypothesized that a daily dose of either 2.4 mg or 3.2 mg lofexidine will achieve greater efficacy than placebo with respect to overall symptom relief over the first 7 days of opioid withdrawal (primary endpoint) and will increase the likelihood of subjects completing Days 1-7 of treatment (secondary endpoint). Further, safety measures in the 2.4 mg and 3.2 mg total daily dose groups will be compared descriptively to assess whether the lower dose results in fewer and less severe adverse events than does the higher dose.

#### 17.2.1 Analysis Populations

Three principal analysis populations are defined as follows:

- Intent-to-treat (ITT), consisting of all randomized subjects. Subjects will be assigned for analysis according to the group to which they are randomized.
- Modified intent-to-treat (mITT), consisting of all subjects in the ITT group who received at least one dose of study medication.
- Safety consisting of all subjects who received at least one dose of study medication.

The principal analysis population for the analyses of demographics and baseline characteristics and efficacy will be the mITT population. Sensitivity analyses of the completion status endpoint will be carried out on the ITT population. Safety summaries will be provided for the Safety population. Data recorded on subjects who are in the ITT but not in the mITT or Safety populations will be included in data listings.

#### 17.2.2 Demographics and Baseline Characteristics

Demographics and baseline characteristics will be summarized descriptively.

### 17.2.3 Subject Disposition

Subject disposition will be summarized descriptively.

### 17.2.4 Primary Efficacy Endpoint

The primary efficacy endpoint is:

- AUC based on SOWS-Gossop scores from Days 1 through 7.

### 17.2.5 Secondary Efficacy Endpoint

The secondary efficacy endpoint is:

- Completion status (i.e., whether a subject receives at least one dose of study medication on Day 7 and completes the 3.5-hour post-dose SOWS-Gossop assessment on Day 7).

### 17.2.6 Tertiary/Exploratory Endpoints

The tertiary/exploratory endpoints are:

- SOWS-Gossop, OOWS-Handelsman, MCGI (Subject and Rater), VAS-E, and COWS scores on Days 1, 2, 3, 4, 5, 6, and 7;
- Retention analysis (time to removal from study treatment) over the 7 inpatient days;
- Concomitant medication analysis;
- Withdrawal-related AE analysis;
- Evaluation of subject treatment status 30 days after last dose;
- Status of detoxification on Day 7 or early termination as assessed by the Site Investigator; and
- In addition, single items (e.g., sweating, anxiety) from the OOWS-Handelsman and COWS that are not included in the SOWS-Gossop may be analyzed, as may AUC based on COWS scores from Days 1 through 7.

### 17.2.7 Control of the False Positive Rate and Statistical Testing Strategy

All statistical tests for efficacy will be one-sided. For the primary and secondary endpoints, the treatment comparisons subject to control of the false positive rate will be 3.2 mg lofexidine vs. placebo and 2.4 mg lofexidine vs. placebo. (Comparisons of 3.2 mg vs. 2.4 mg will be descriptive.) The familywise error rate (FWE) for the collection of primary and secondary endpoint comparisons will be controlled at the 0.025 level, one-sided, by a sequential testing strategy in which hypotheses are tested in the following order, each at the 0.025 level, one-sided.

1. Primary: AUC(1-7), 3.2 mg lofexidine versus placebo;
2. Primary: AUC(1-7), 2.4 mg lofexidine versus placebo;
3. Secondary: Completion rate, 3.2 mg lofexidine versus placebo; and

## 4. Secondary: Completion rate, 2.4 mg lofexidine versus placebo.

Adjusted p-values for these 4 treatment comparisons, based on this sequence of statistical tests, are defined in the table below.

Test Order	Endpoint Comparison	P-value	
		Unadjusted (a)	Adjusted
1	AUC(1-7), 3.2 mg vs placebo	$p_1$	$p_1$
2	AUC(1-7), 2.4 mg vs placebo	$p_2$	$\max(p_1, p_2)$
3	Completion rate, 3.2 mg vs placebo	$p_3$	$\max(p_1, p_2, p_3)$
4	Completion rate, 2.4 mg vs placebo	$p_4$	$\max(p_1, p_2, p_3, p_4)$

(a) P-values  $p_1$  and  $p_2$  are one-sided, derived from the statistical test described in [Section 17.2.8.1](#);  
p-values  $p_3$  and  $p_4$  are one-sided, derived from the statistical test described in [Section 17.2.8.2](#).

Any adjusted p-value less than 0.025 in magnitude will be declared statistically significant.

The tertiary/exploratory endpoints will be tested without multiplicity adjustment.

## 17.2.8 Statistical Methods for Efficacy

### 17.2.8.1 SOWS-Gossop AUC(1-7)

A pattern-mixture approach [21], with subjects stratified by disposition within Days 1-7, will be used in assessing SOWS-Gossop AUC(1-7). The 4 disposition strata are subjects: who complete Days 1-7 of the study (see [Section 17.2.5](#)); who discontinue due to lack of efficacy (including adverse events related to opioid withdrawal); who discontinue due to adverse events related to intolerability or toxicity to study drug; and who discontinue for other reasons. The inference is comprised of several steps:

1. Transformation. Because of the inherent skewness in the SOWS-Gossop scores the raw data will first be transformed to the logarithm of the score plus 1.0.
2. Modeling. A linear mixed effects repeated-measures model will be constructed for the SOWS-Gossop score. The fixed effects will be disposition stratum, treatment and time, and their interactions, as well as a main effect of gender (randomization stratification factor) and baseline SOWS-Gossop score as a one degree of freedom covariate. For each combination of treatment and stratum, the time course will be modeled as a linear change point model, allowing for one slope between Days 1 and 2 and a possibly different slope from Days 2 through 7. The model will be parameterized to ensure that the predictions from the two line segments agree at Day 2. Subjects will be treated as a random effect, and the slope and intercept parameters will be treated as random coefficients. Modeling the time course, rather than using each time point as a discrete level of a model factor, allows estimation of group means through Day 7 even in the non-completer strata. The choice of Day 2 as the change point is based on prior lofexidine studies, in which SOWS-Gossop mean scores in the placebo group increased from Day 1 to Day 2 and then decreased through Day 7. The modeling allows a different time course for each of the lofexidine dose groups.

3. Point estimates of AUC(1-7). For each combination of disposition stratum, treatment and study day, the estimated least squares means SOWS-Gossop (on the log scale) for males and females will be combined using a weighted average, the weights being the relative proportions of males and females in the mITT population. The results will then be transformed back to the original SOWS-Gossop scale of measurement, from which point estimates of AUC(1-7) for each combination of stratum and treatment will be computed using the trapezoidal rule. It should be noted that these calculations will not be derived from AUC(1-7) computed within individual subjects, many of whom will have incomplete data for the later study days in Days 1-7. In particular, there will be no imputation of data for individual subjects.
4. Estimates of treatment effect. For each active treatment, the treatment effect (lofexidine 3.2 mg versus placebo or lofexidine 2.4 mg versus placebo) will be estimated with respect to AUC(1-7) within each disposition stratum. Then a weighted average of treatment effects will be computed, where the weights are the relative proportions of subjects in the 4 strata.
5. Interval estimates of AUC(1-7) and hypothesis testing. The covariance matrix of the mixed model's estimated fixed effects will be used with standard linear model methods to derive the covariance matrix of the weighted average of male and female log-transformed SOWS-Gossop scores. The multivariate delta method will be used to derive the covariance matrix of the back-transformed SOWS-Gossop time course. Standard linear model methods will then be used to derive the covariance matrix of the weighted average of AUC(1-7) treatment effects, from which confidence intervals and p-values will be derived.

#### 17.2.8.2 Completion Status

The proportion of subjects in each treatment arm who receive at least one dose of study medication on Day 7 and complete the 3.5-hour post-dose SOWS-Gossop assessment on Day 7 will be analyzed using Cochran-Mantel-Haenszel tests, with gender as the stratifying factor. One test will compare the 3.2 mg lofexidine group to placebo; a second will compare the 2.4 mg lofexidine group to placebo.

#### 17.2.8.3 SOWS-Gossop on Days 1, 2, 3, 4, 5, 6, and 7

The pattern-mixture approach, with the same stratification and treatment of gender used for the AUC(1-7) analysis, will be used to assess treatment effect with respect to SOWS-Gossop on Days 1, 2, 3, 4, 5 and 6 (but not 7). A single linear mixed effects repeated-measures model will be constructed for the transformed SOWS-Gossop score. Subject will be a random effect. The fixed effects will be disposition stratum, treatment and time, with each study day as a discrete level of the time factor, and their interactions. Estimated means for each combination of stratum, treatment and day will be back-transformed to the original SOWS-Gossop scale of measurement. Like the AUC(1-7) calculation, the weighted average of treatment effects will be calculated along with confidence intervals and p-values. This approach will provide no information on the non-completer strata on Day 7. Therefore, the modeled time course from the AUC(1-7) analysis will be used to estimate SOWS-Gossop on Day 7 for all combinations of disposition stratum and treatment, and Day 7 comparisons will be based on these estimates.

#### 17.2.8.4 *OOWS-Handelsman, MCGI (Subject and Rater), VAS-E, and COWS*

The same methods used for SOWS-Gossop on Days 1, 2, 3, 4, 5, 6, and 7 will be used for OOWS-Handelsman, MCGI (Subject and Rater), VAS-E, and COWS scores on Days 1, 2, 3, 4, 5, 6, and 7. Types of data transformation, if any, to be used before mixed effects modeling, will be specified in the SAP.

#### 17.2.8.5 *Retention Analysis (Time to Removal from Study Treatment)*

Time to removal from study treatment is defined as the last study day on which the subject received treatment. The time for subjects who complete some but not all treatment on Day 7 will be Day 7, uncensored. Subjects who complete all treatments on Day 7 will be censored at Day 7. This endpoint will be summarized descriptively for each combination of treatment group and gender with Kaplan-Meier curves and tabulations of the number and percentage of subjects newly removed from receiving study treatment on each of inpatient Days 1 to 7. Each lofexidine dose group will be compared inferentially to placebo with a Cox proportional hazards regression model of time to removal from study, stratified by gender, with treatment as the independent variable. The estimated hazards ratio will be reported as a descriptive measure. The p-value on the log hazards ratio will be converted to a one-tailed p-value by considering whether the hazard ratio indicates a delay in time to removal in the lofexidine group versus the placebo group.

#### 17.2.8.6 *Concomitant Medication Analysis*

For each of Days 1 to 7, each subject's number of concomitant medication doses taken will be treated as a continuous variable. Descriptive statistics will be provided on the as-observed data on each study day. In addition, least squares means and p-values comparing each treatment to placebo will be obtained with the same methods used for SOWS-Gossop on Days 1, 2, 3, 4, 5, 6, and 7. Types of data transformation, if any, to be used before mixed effects modeling, will be specified in the SAP.

#### 17.2.8.7 *Status of Detoxification on Day 7 or Early Termination as Assessed by the Site Investigator*

Descriptive statistics (numbers and percentages) on the status of detoxification (successful/unsuccessful) as assessed by the Site Investigator at Day 7 or early termination will be presented by treatment group overall and by gender within treatment group.

#### 17.2.8.8 *Single Items from the OOWS-Handelsman and COWS, and COWS AUC(1-7)*

Single items (e.g., sweating, anxiety) from the OOWS-Handelsman and COWS that are not included in the SOWS-Gossop may be analyzed; the scores will be treated as continuous variables and analyzed using the same methods used for SOWS-Gossop on Days 1, 2, 3, 4, 5, 6, and 7. COWS AUC(1-7) may also be analyzed; a modeling approach analogous to the modeling of SOWS-Gossop AUC(1-7) will be used. While the functional form of the time course for SOWS-Gossop is based on historical data, the functional form of the time course for COWS will be based on the data from this study.

### 17.2.9 Power Calculations

Treatment effect and subject variability with respect to SOWS-Gossop scores were estimated from the prior Phase 3 study (USWM-LX1-3002), using the random coefficients model planned for the present study and estimating the treatment effect of 3.2 mg lofexidine versus placebo with respect to AUC(1-7). It was assumed that the treatment effect of the 2.4 mg lofexidine dose will be three-fourths the treatment effect of the 3.2 mg dose. The table below shows the power to find a significant treatment effect for the comparisons of the two lofexidine treatments versus placebo, assuming a sample size allocation ratio of 3:3:2 (3.2 mg lofexidine : 2.4 mg lofexidine : placebo) and accounting for the sequential testing approach described in [Section 17.2.7](#). The power to find a statistically significant effect of the 3.2 mg lofexidine dose with respect to AUC(1-7) is in excess of 90% with the planned total sample size of 600.

Total Sample Size	Power (%) with Respect to AUC(1-7)	
	3.2 mg Lofexidine versus Placebo	2.4 mg Lofexidine versus Placebo
600	94.6	72.6
550	92.6	67.6
500	90.1	62.2
450	86.8	55.7

### 17.2.10 Subgroup Analyses

The models used for the primary analysis will be modified for each of several subgroups to include the subgroup and its interaction with treatment as a fixed effect. Subgroups include age, gender, and race. The SAP will list all subgroups to be analyzed, their classifications (e.g., age dichotomization, race groupings), and modeling details.

### 17.2.11 Safety Measures

The safety measures during Days 1-7 of the study are AEs, vital signs, ECGs (primarily evaluated for changes in QTcF versus time-matched controls for both doses of lofexidine and placebo), clinical laboratory measures, physical exams, and suicidal ideation and behavior. Adverse event summaries will include tabulations overall and by seriousness, severity, and causality assessment. The data from these measures recorded during Days 1-7 will be summarized descriptively by treatment group. In addition, each lofexidine group will be compared inferentially to the placebo group using chi-square tests for categorical variables and t-tests within an analysis of variance for continuous variables; the resulting p-values will not be adjusted for multiple testing.

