- (j) Vital signs (resting [sitting/recumbent] and standing blood pressure, and pulse) will be measured at least once daily before dosing and 3.5 hours after dosing on Days 8-13 and once before any dose on Day 14. Oral temperature and respiration are not required measurements Days 8-14. Note that if subjects are being treated on an outpatient basis and cannot stay in the clinic for measurement of the 3.5-hour post-dose vital signs required on Days 8-13, they will be given a portable digital blood pressure machine for measurement of their vital signs at this required time point. They will also be provided a diary to record the measurements.
- (k) Baseline 12-lead electrocardiograms (ECGs) will be done on one day during the screening period, time-matched to the post randomization ECG schedule (i.e., pre-1 PM [before 1 PM dose], 4 PM [3 hours post-dose], and 5 PM [4 hours post-dose]).
  - (l) 12-lead ECGs will be done before the first daily dose, pre-1 PM dose, at 4 PM, and at 5 PM on Days 1 and 7; and before the first daily dose only on Days 2 and 4.
  - (m) 12-lead ECGs will be done before the first daily dose and 3.5 hours after first daily dose on Day 8; on Day 14, the ECGs will be done before a dose on that day.
  - (n) A finger prick blood sample will be collected concurrently with each scheduled ECG during Days 1-7.
  - (o) Clinical lab testing will be done as clinically warranted throughout the study and at the end of double-blind dosing and before initiating open-label dosing.
  - (p) A complete physical examination will be performed during screening and the physical exam form will be updated at Baseline. A complete physical examination will be performed on Day 1 (3-4 hours after randomization) and at the end of double-blind dosing and before initiating open-label dosing. During Days 8-14, a complete physical exam will be performed as clinically warranted and at discontinuation from the study.
  - (q) Urine drug screen will be done at least every other day to monitor for contraband (inpatient setting) or illicit (outpatient setting) drug use.
  - (r) A finger prick blood sample will be collected at 9 PM and 10 PM (3 and 4 hours, respectively, after the 6 PM dose).

209229

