6.2 Derived Data

• Definition of baseline

For all variables, baseline is defined as the last non-missing value prior to the receiving the first dose of study medication.

All tabulations involving change from baseline data will only include subjects with cohort data i.e. with data at baseline and at follow-up. Change from baseline will be calculated as follow-up values minus baseline value.

• Incomplete dates

All incomplete dates will be included in the clinical database as they were entered in the eCRF. Thereafter for calculation purposes, the incomplete dates will be completed using pre-defined rules. If a day or month is not recorded it will be replaced by the first day of the month or January respectively, provided this does not contradict any other dates recorded. For missing adverse events and medications dates/times during the trial, the worst-case date will be used (e.g. the end of the month for a stop date and 23:59 for the stop time, the date/time of initial dose for start of AE i.e. all events with missing start dates will be assumed to be treatment emergent).

• Ambiguous values

In the case where a variable is recorded as ">x", " \geq x", "<x" or " \leq x", then for analysis purposes a value of x will be taken. Where a range of values is quoted the midpoint of the range will be taken.

Effective: 14-Feb-13

Page 6 of 26

• Questionnaire Data

In the event that component items used to calculate total scores for questionnaire data e.g. SOWS Gossop score are missing then the total scores will also be set to missing.

• Site pooling for statistical analyses

For the purposes of statistical analyses models where site is included within the model as a fixed effect, sites randomizing < 6 subjects will be pooled from smallest to largest until the pooled site subsequently created has at least 6 subjects. In the event that the pooling of sites with less than 6 subjects does not result in a site with > 6 subjects, then that pooled site with < 6 subjects will also be pooled with the next largest site with > 6 subjects. To break ties if more than one site has the same number of subjects, the site identifier will be used as a secondary sort key.

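### The time-matched QTcF evaluation names no control for the pre-first-dose ECGs of Days 2, 4 and 7, and the SAP's general baseline, if it applies to ECG, matches only those three readings

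*Protocol*

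**What the plan says.** Protocol 17.2.11 (Safety Measures) sets the evaluation: "ECGs (primarily evaluated for changes in QTcF versus time-matched controls for both doses of lofexidine and placebo". It then says that "each lofexidine group will be compared inferentially to the placebo group using chi-square tests for categorical variables and t-tests within an analysis of variance", the second of these being the method for continuous measures such as QTcF. It names no covariates and does not define the time-matched control.

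Table 1, note k: "Baseline 12-lead electrocardiograms (ECGs) will be done on one day during the screening period, time-matched to the post randomization ECG schedule". The times are "pre-1 PM [before 1 PM dose], 4 PM [3 hours post-dose], and 5 PM [4 hours post-dose". Sections 15.1 and 15.5.3 give the same three times.

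Table 1, note l, sets four blinded ECG times a day at the start and end of the week: "before the first daily dose, pre-1 PM dose, at 4 PM, and at 5 PM on Days 1 and 7". In between it schedules a single daily reading on two days: "before the first daily dose only on Days 2 and 4". Section 14.3.3 places the first dose in the 8 AM window on Day 1, so the Day 1 pre-first-dose tracing is untreated.

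SAP 6.2: "For all variables, baseline is defined as the last non-missing value prior to the receiving the first dose of study medication". SAP 6.13 sends the ECG data to a separate report and keeps only a listing of the investigator's overall interpretation. SAP 6.14, which lists departures from the protocol's analyses, contains nothing on 17.2.11.

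**The concern.** A change in QTcF needs a stated pre-drug value for each reading. The protocol points to screening ECGs that lack a pre-first-dose time, yet on Days 2 and 4 that is the only scheduled ECG. With screening controls alone, no scheduled reading between Day 1 and Day 7 enters the time-matched evaluation.

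The SAP's general rule points elsewhere, to one tracing shortly before 8 AM on Day 1. Under it, the 4 PM and 5 PM readings, which the protocol places 3 and 4 hours after the 1 PM dose, become afternoon-minus-morning changes within each arm. The two rules give different QTcF changes for the same subject, and the documents do not say which applies.

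A smaller point concerns efficiency. The stated comparison with placebo uses neither the matched pre-drug QTcF as a covariate nor gender, although gender is the randomisation stratum (Protocol 14.3.2).

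**Working it through.** The plan gives no figure on this point to reproduce. The check counts scheduled ECG times and compares clock times.

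**Inputs.** Screening times: pre-1 PM, 4 PM, 5 PM (Table 1, note k). Blinded times: four on each of Days 1 and 7, one on each of Days 2 and 4 (note l). First dose: 8 AM window on Day 1 (14.3.3).

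**Step 1: count.** 4 + 4 + 1 + 1 = 10 scheduled times. The Day 1 pre-first-dose ECG precedes drug, which leaves 9 on-treatment times.

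**Step 2: match by clock time.**

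| Day | On-treatment times | Match to screening | Match to Day 1 pre-first-dose |
|---|---|---|---|
| 1 | pre-1 PM, 4 PM, 5 PM | 3 of 3 | 0 of 3 |
| 2 | pre-first-dose | 0 of 1 | 1 of 1 |
| 4 | pre-first-dose | 0 of 1 | 1 of 1 |
| 7 | pre-first-dose, pre-1 PM, 4 PM, 5 PM | 3 of 4 | 1 of 4 |
| Total | 9 | 6 of 9 | 3 of 9 |

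Neither rule alone covers all nine. Together they cover 6 + 3 = 9 of 9.

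**Step 3: clock offset under SAP 6.2.** Against a tracing at about 8 AM, the pre-1 PM, 4 PM and 5 PM readings are about 5, 8 and 9 hours away.

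**Step 4: effect of the offset.** Let d be the ordinary shift in QTcF between early morning and the afternoon reading. The documents give no value; I assume 3 to 10 msec for scale. If the time-matched change is L on lofexidine and P on placebo, the SAP 6.2 changes are L + d and P + d. Each within-arm mean is off by d. The difference is (L + d) - (P + d) = L - P, so the shift cancels.

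**Step 5: precision of the placebo comparison.** With equal variance s² before and on treatment and correlation r, the variance of a change score is 2s²(1 - r). The residual variance after covariate adjustment is s²(1 - r²). The ratio of standard errors is sqrt((1 - r²)/(2(1 - r))) = sqrt((1 + r)/2).

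- r = 0.5: sqrt(0.75) = 0.866, a 13% smaller standard error.
- r = 0.7: sqrt(0.85) = 0.922, an 8% smaller standard error.

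Both correlations are assumptions. The calculation covers the pre-drug QTcF only; no gain is quantified for gender.

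**The case against.** **The ECG method may simply be elsewhere.** SAP 6.13 places ECG outside this SAP, and the SAP does depart from 6.2 where it chooses: Addendum 1, Change 15, measures vital-sign change from screening. A reader might infer that SAP 6.2 overrides the protocol's time-matched control, and the documents do not establish that. The gap remains, because the separate report's method is neither given nor cited, the exception written for vital signs was not written for ECG, and 17.2.11 stands unchanged.

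**The controls could be concurrent placebo subjects.** Same-time placebo readings do exist at every time point. However, 17.2.11 lists placebo among the groups evaluated against controls and gives the comparison with placebo its own sentence, so untreated readings in the same subject are the natural meaning. On either reading, a change still needs a baseline.

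**No data are lost.** This stands. A reader might infer that the change cannot be computed, but the Day 1 pre-first-dose tracing supplies the missing match. A reader might also infer that QTcF after Day 1 would be known only in subjects still present on Day 7. That goes too far: 15.3.3 and 15.5.3 call for an ECG at early termination, and 17.2.11 summarises the Days 1-7 safety data descriptively, so Day 2 and Day 4 values are still reported. What they lack is a named control.

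**ANCOVA is a preference.** In part. If change is analysed, the matched value is already subtracted, and under randomisation both methods are unbiased. These safety p-values are also unadjusted for multiplicity. The gain is precision only, but it needs no new data.

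**Conclusion.** The point holds as a gap in specification. Three of the nine scheduled on-treatment readings have no named control under the protocol. The SAP's general baseline, if it governs ECG, would leave the other six unmatched. The counts rest on the documents alone.

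The consequence is limited. Screening controls already give the planned change for every 4 PM and 5 PM reading on Days 1 and 7. Any time-of-day shift affects within-arm changes under SAP 6.2 by an amount the documents do not state. A reader might infer a biased lofexidine-placebo difference, but the shift is common to the arms and cancels.

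The 8 to 13% reduction in standard error depends on an assumed baseline correlation of 0.5 to 0.7 and equal variances. It does not make the stated t-test invalid.

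**What to change.** In Protocol 17.2.11 and SAP 6.2 and 6.13:

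1. Exempt ECG from the SAP 6.2 baseline, and cite the plan for the stand-alone ECG report.
2. Define the control by clock time: the screening ECG of the same time for the pre-1 PM, 4 PM and 5 PM readings, and the Day 1 pre-first-dose ECG for later pre-first-dose readings.
3. Report early-termination and Day 8 post-dose ECGs, which have no exact clock-time match, against a stated nearest-time control.
4. Compare each dose with placebo on QTcF change by ANCOVA, with the matched pre-drug QTcF and gender as covariates, in place of "t-tests within an analysis of variance for continuous variables" for this variable.

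In the same edit, reconcile Protocol 15.5.3, which assigns the Bazett correction to analysis and Fridericia to safety monitoring, with the QTcF evaluation in 17.2.11.

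The cost is wording in the protocol, SAP and ECG report plan. The control tracings are already scheduled, so no visit or procedure is added.
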